5.2.5 End of Study

The following will be undertaken 28 days after last dose of study medication:

- Vital signs including blood pressure, pulse, respiratory rate, body weight, and height
- Karnofsky or ECOG performance status
- Complete physical examination and toxicity evaluation (CTCAE v 4.0)
- Update concomitant medications
- Compete blood count with differential and platelets
- Comprehensive Metabolic Panel: sodium, potassium, chloride, bicarbonate, BUN, creatinine, calcium, alanine aminotransferase, aspartate aminotransferase, alkaline phosphatase, total bilirubin, albumin
- Magnesium, phosphorous, LDH, thyroid stimulating hormone
- Fasting lipid panel
- Urinalysis
- Urine protein & creatinine

This visit can be foregone for patients who are too unwell to attend or for other reasons at the investigators discretion. Patients may be contacted thereafter by phone to assess resolution of toxicities, and may be contacted for survival follow up.

5.3 Agent Administration

Pazopanib and everolimus may be taken at the same time. Patients will be instructed to take the everolimus AND Pazopanib at the same time every morning, without food, at least one hour before or two hours after a meal. Before discharge from the clinic, subjects

will be given a study dosing diary to take home. The subject will be instructed to record the date and time that each dose of pazopanib and everolimus is self administered. Study diaries will be reviewed and collected at each visit during the remainder of the study.

5.3.1 Pazopanib

Pazopanib will be self administered (by the patients themselves). Pazopanib will be administered orally as once daily dose continuously from study day 1 until progression of disease or unacceptable toxicity. Pazopanib should be taken orally without food at least one hour before or two hours after a meal. The tablets should be swallowed whole and must not be crushed or broken. The time of day the tablets are taken should be relatively constant. Dietary habits around the time of pazopanib intake should be as consistent as possible throughout the study. If a dose is missed, the subject should take the dose as soon as possible, but not if there are less than 12 hours before the next dose is due. If the next dose is due in less than 12 hours, the subject should skip the missed dose and take the next dose as scheduled.

If vomiting occurs after taking pazopanib, another dose is not permitted on that day. The subject should resume taking pazopanib at the next scheduled dose. If vomiting persists, the subject should be instructed to notify the investigator.

5.3.2 Everolimus

Dosing regimen

The investigator should promote compliance by instructing the patient to take the study drug exactly as prescribed and by stating that compliance is necessary for the patient's safety and the validity of the study. The patient should be instructed to contact the investigator if he/she is unable for any reason to take the study drug as prescribed.

Everolimus should be administered orally once daily at the same time every day, without food, at least one hour before or two hours after a meal, at the same time as the Pazopanib. If a dose is missed, the subject should take the dose as soon as possible, but not if there are less than 12 hours before the next dose is due. If the next dose is due in less than 12 hours, the subject should skip the missed dose and take the next dose as scheduled.

Tablets

The tablets should be swallowed whole with a glass of water and should not be chewed or crushed. For patients unable to swallow tablets, the tablet(s) should be dispersed completely in a glass of water (containing approximately 30 mL) by gently stirring, immediately prior to drinking. The glass should be rinsed with the same volume of water and the rinse completely swallowed to ensure the entire dose is administered.

If vomiting occurs, no attempt should be made to replace the vomited dose.

5.4 Definition of Dose-Limiting Toxicity

5.4.1 Dose escalation rules

General rules:

- Initial dose is dose level 0 for this trial
- All patients in a dose cohort will complete 28 days (1 cycle) of combination treatment prior to the treatment of any patient at a higher dose level.
- If a patient does not complete the 28 days of treatment for reasons that are clearly not adverse events related to treatment, then that patient will be replaced, up to three per dose level.
- If more than three patients need to be replaced on a dose level, then the reasons will be re-evaluated before continuing.
- There will be no intrapatient dose escalation.
- To determine that a subject has received study treatment without experiencing DLT, the subject must have missed no more than 5 days of dosing during cycle 1, either nonconsecutively or consecutively.

Pazopanib and everolimus doses will be escalated according to the following standard 3+3 dose escalation rules:

1. If 0 of 3 patients in a cohort experience dose limiting toxicities, then the next cohort of 3 patients will be treated at the next higher dose level.
2. If 1 of 3 patients in a cohort experiences a DLT then the cohort will be expanded to treat an additional three patients. If only one of 6 patients experiences a DLT, then the next cohort of patients will be treated at the next higher dose level.
3. If two or more patients in a cohort experience a DLT, then the MTD has been exceeded. The previous dose level will be considered the MTD. If only 3 patients were treated at the previous dose level, an additional three patients will be treated at that dose level to confirm the MTD.
4. If the doses of both drugs are escalated to dose level 2 with 0 of 3 or 1 out of 6 patients experiencing a DLT, then this will be considered the recommended Phase II dose (RP2D) for the expansion cohort.
5. If the MTD is exceeded on dose level 0, then a de-escalation cohort to dose level -1 will be enrolled. Up to six patients will be treated at this dose level. If one or fewer of six patients experiences a DLT, then this will be the RP2D. If two or more patients experience a DLT on dose level -1, then the combination will be deemed not feasible and the study will be closed.
6. If the MTD is exceeded on dose level 2, then a de-escalation level will be accrued (dose level 2A). If 0 of 3 or 1 out of 6 patients experience a DLT on dose level 2A,

then this will be considered the RP2D for the expansion cohort. If the MTD is exceeded on dose level 2A, then dose level 1 will be the RP2D.

5.4.2 Definition of a DLT

Dose-limiting toxicity (DLT) is based on the CTEP Active Version of the NCI Common Terminology Criteria for Adverse Events (CTCAE v4.0).

For the purposes of Phase I dose escalation, a DLT will be defined as toxicity occurring within the first 28 days of combination therapy related to therapy that meets the criteria spelled out below:

1. Grade 3 or 4 non-hematologic toxicity excluding:
 - Toxicity attributed to underlying malignancy
 - Nausea/vomiting controlled with antiemetics
 - Grade 3 hypertension that resolves to $\leq 150/90$ within 7 days of adjustment or addition of oral blood pressure medications.
 - a. Hypertension that requires admission to the hospital or intravenous medication for control will be considered a DLT.
 - b. Grade 3 or greater hypertension that does not respond to adjustment or addition of oral blood pressure medicines to $\leq 150/90$ within 7 days from blood pressure medication modification will be considered a DLT.
 - Grade 3 asymptomatic, clinically insignificant laboratory abnormalities, including LDH, alkaline phosphatase due to bone metastases, and asymptomatic hypophosphatemia
2. Hematologic toxicity defined as:
 1. Grade 4 thrombocytopenia or grade 3 thrombocytopenia with bleeding
 2. Grade 4 neutropenia which persists for >7 days
 3. Grade 4 neutropenia associated with fever $>38.5^{\circ}\text{C}$
 4. Excludes lymphopenia or anemia of any grade
3. Removal of a patient from therapy due to toxicity attributable to treatment
4. Patients who miss more than 5 days of the planned doses for drug-related intolerable grade 2 toxicity will be considered to have experienced a DLT. During cycle 1, patients who miss fewer than 5 days of dosing for drug-related toxicities that do not immediately meet the criteria for DLT must recover to \leq grade 1 within two weeks, or they will be considered to have experienced DLT.
5. Toxicity related to therapy severe enough to require a dose-reduction

Management and dose modifications associated with the above adverse events are outlined in Section 6 (Expected Toxicities and Dosing Delays/Dose Modifications).

5.5 General Concomitant Medication and Supportive Care Guidelines

5.5.1 Patients should receive full supportive care, including analgesic medication, transfusions of blood and blood products, antibiotics, antiemetics, etc., when appropriate. Although acetaminophen at doses of ≤ 2 g/day is permitted, it should be used with caution in subjects with impaired liver function. Anti-diarrheals, such as loperamide, may be administered as needed in the event of diarrhea. The reason(s) for treatment, dosage, and the dates of treatment should be recorded in the medical record.

5.5.2 Palliative radiation therapy may not be administered while the patient is on study treatment. A symptomatic lesion or one which may produce disability (e.g., unstable femur) may be irradiated before study initiation, provided other measurable or evaluable disease is present and radiation therapy is completed ≥ 4 weeks before start of therapy. All eligibility criteria for progression must still be met. Any other indications for radiotherapy after protocol treatment has begun will constitute disease progression, and the patient will stop protocol treatment.

5.5.3 Erythropoetin/ Darbepoetin: Use of erythropoietin or darbepoetin in this protocol is permitted at the discretion of the treating physician after cycle 1 (ie., after the DLT determination period).

5.5.4 Filgrastim (G-CSF), pegfilgrastim, and sargramostim (GM-CSF) after cycle 1 (ie. After the DLT determination period)

1. Filgrastim/pegfilgrastim and sargramostim should not be used to avoid dose reductions.
2. Filgrastim, pegfilgrastim, or sargramostim, may be used for secondary prophylaxis following an episode of febrile neutropenia.
3. For the treatment of febrile neutropenia, the use of CSF's should not be routinely instituted as an adjunct to appropriate antibiotic therapy. However, the use of CSF's may be indicated in patients who have prognostic factors that are predictive of clinical deterioration such as pneumonia, hypotension, multi-organ dysfunction (sepsis syndrome) or fungal infection, as per the ASCO guidelines. Investigators should therefore use their own discretion in using the CSF's in this setting. The use of CSF (filgrastim, pegfilgrastim or sargramostim) must be documented and reported in the medical record.
4. If filgrastim, pegfilgrastim or sargramostim are used, they must be obtained from commercial sources.

5.5.5 Drug Interactions

Because there is a potential for interaction of pazopanib and Everolimus with other concomitantly administered drugs through the cytochrome P450 system, the case report form must capture the concurrent use of all other drugs, over-the-counter medications, or alternative therapies. The Principal Investigator (or

Protocol Chair) should be alerted if the participant is taking any agent known to affect or with the potential to affect selected CYP450 isoenzymes.

5.5.1 Permitted Medications

All subjects will be asked to provide a complete list of prescription and over-the-counter medications that have been taken within the 4 weeks prior to screening. The investigator must be informed as soon as possible about any new medication(s) taken from the time of screening until the completion of the post-treatment follow-up visit. All concomitant medications taken during the study will be recorded in the case report form (CRF) with indication, dose information, and dates of administration.

5.5.2 Permitted Medications – Use with Caution

- Specific recommendations regarding anticoagulants:**

Results from drug-drug interaction studies conducted in subjects with cancer suggest that pazopanib has no effect on the metabolism of S-warfarin. Hemorrhagic events, however, have been reported in clinical studies with pazopanib; therefore, pazopanib should be used with caution in subjects with increased risk of severe bleeding or who are receiving concomitant anticoagulant therapy (e.g., warfarin or its derivatives, low molecular weight heparin, unfractionated heparin). Subjects taking concomitant anticoagulant therapy should be monitored regularly for changes in relevant coagulation parameters as clinically indicated, as well as for any clinical bleeding episodes.

Oral anticoagulants such as warfarin are CYP2C9 substrates and, as such, no interaction with everolimus is expected. However, drug-drug interaction studies between macrolide antibiotics and warfarin have produced mixed outcomes and the disparity in these findings has led to the conclusion that multiple factors may alter the clearance of warfarin. The co-administration of everolimus and oral anticoagulants is possible but should be subject to verification of coagulation (INR) once steady state is reached (after one week's treatment).

- Specific recommendations regarding hypoglycemic therapy including insulin:**

Results from drug-drug interaction studies conducted in subjects with cancer suggest that there will be no clinically relevant pharmacokinetic interaction between pazopanib and hypoglycemic agents. Transient decreases in serum glucose (mainly Grade 1 and 2, rarely Grade 3) have been observed in clinical studies with pazopanib. In addition, decreases in blood sugar have been recently reported in subjects treated with another small molecule tyrosine kinase inhibitor, sunitinib (British Journal of Cancer 2008: 99, 1380). Such changes may require an adjustment in the dose of hypoglycemic and/or insulin therapy. Subjects should be advised to report symptoms of hypoglycemia (e.g., confusion, visual disturbances, palpitations, sweating). Serum glucose should be tested during treatment with pazopanib as outlined in the protocol and as clinically indicated.

- **Specific recommendations regarding oral hypoglycemics:** Co-administration of pazopanib with some oral hypoglycemics, including glipizide, glyburide (glibenclamide), glimepiride, nateglinide, repaglinide, gliclazide, acetohexamide, carbutamide, glibornuride, glymidine, metahexamide, and tolazamide, may result in an increase in plasma concentrations of the oral hypoglycemic agent. This increase may result in hypoglycemia. Therefore, the dose of the oral hypoglycemic agent should be reduced by 50% when pazopanib administration starts. The blood glucose should be monitored closely, and the subject should be instructed to measure their blood glucose if they experience symptoms of hypoglycemia and inform their physician if their blood glucose concentration is low. After at least 14 days of pazopanib administration, the dose of the oral hypoglycemic agent may be increased as necessary to maintain adequate blood glucose control.
- **The Effects of Pazopanib on Other Drugs**
In vitro data indicate that pazopanib is a potential inhibitor for CYP3A4, CYP2C8, CYP2D6, CYP1A2, CYP2C9, CYP2C19, CYP2A6, CYP2B6, and CYP2E1. Pregnen X receptor transient transfection assay suggested some potential for human CYP3A4 induction at high concentrations. Results from drug-drug interaction studies conducted in subjects with cancer suggest that pazopanib is a weak inhibitor of CYP3A4, CYP2C8, and CYP2D6 *in vivo*, but had no clinically relevant effect on CYP1A2, CYP2C9 or CYP2C19 metabolism. Therefore, concomitant use of pazopanib with certain medications (substrates of CYP3A4, CYP2C8, and CYP2D6) with a narrow therapeutic window should be undertaken with **CAUTION** due to the potential for alterations in the pharmacologic effects of these medications or an increased risk for serious or life threatening adverse events associated with such medications (see below) secondary to the inhibition of specific CYP enzymes by pazopanib. In addition, the potential for drug interaction with such medications, although diminished, may persist after the last dose of pazopanib due to its long half-life (i.e., mean 30.9 hours); therefore, continue to exercise **CAUTION** for at least 7 days and up to 15 days after the last dose of pazopanib when administering these medications. These medications include (but are not limited to):
 - Ergot derivatives: dihydroergotamine, ergonovine, ergotamine, methylergonovine (potential increased risk for developing ergot toxicity that includes severe vasospasm leading to peripheral as well as cerebral ischemia)
 - Neuroleptics: pimozide (potential increased risk for QT interval prolongation, ventricular arrhythmia, and sudden death)
 - Antiarrhythmics: bepridil, flecainide, lidocaine, mexiletine, amiodarone, quinidine, propafenone (potential increased risk for QT interval prolongation and Torsade de Pointes)
 - Immune modulators: cyclosporine, tacrolimus, sirolimus (potential increased risk for nephrotoxicity and neurotoxicity)

- Miscellaneous: quetiapine, risperidone, clozapine, atomoxetine.
- **The Effects of Other Drugs on Pazopanib and Everolimus**
Results from *in vitro* studies suggest that the oxidative metabolism of pazopanib in human liver microsomes is mediated primarily by CYP3A4, with minor contributions from CYP1A2 and CYP2C8. Furthermore, *in vitro* data suggest that pazopanib is a substrate for p-glycoprotein. Substances that induce or inhibit CYP3A4 may alter the pharmacologic effects of pazopanib and should be used with **CAUTION**. Competitive inhibition could occur when everolimus is combined with drugs which are also CYP3A4 substrates. Therefore caution should be exercised in such cases.
 1. Concurrent administration of everolimus and moderate CYP3A4 inhibitors (such as erythromycin, fluconazole, calcium channel blockers, benzodiazepines) and moderate CYP3A4 inducers (e.g. carbamazepine, phenobarbital, phenytoin) should also be avoided if possible, or used subject to caution (e.g. increased frequency of safety monitoring, temporary interruption of everolimus).
 2. Grapefruit and grapefruit juice affect cytochrome P450 and P-glycoprotein activity and should therefore be avoided. In addition, patients should avoid Seville oranges and star fruit, as well as the juice of these fruits, which are potent CYP3A4-inhibitors.

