3.4.16 Liver disease such as chronic cirrhosis, active hepatitis or chronic persistent hepatitis

3.4.17 Uncontrolled diabetes mellitus as defined by HbA1c >8% despite adequate therapy. Patients with a known history of impaired fasting glucose or diabetes mellitus (DM) may be included, however blood glucose and antidiabetic treatment must be monitored closely throughout the trial and adjusted as necessary

3.4.18 Current treatment on another clinical trial within one month prior to dosing.

3.4.19 Pregnant or breastfeeding. Pregnant women are excluded from this study because pazopanib and everolimus are agents with the potential for teratogenic or abortifacient effects. Because there is an unknown but potential risk of adverse events in nursing infants secondary to treatment of the mother with either of these agents, breastfeeding should be discontinued if the mother is treated with either pazopanib or everolimus. These potential risks may also apply to other agents used in this study.

3.4.20 Chronic treatment with systemic corticosteroids or other immunosuppressive agent. Topical or inhaled corticosteroids are allowed.

3.4.21 Patient is unable or unwilling to discontinue predefined prohibited medications listed in the protocol for 4 weeks of a drug or 5 times the half life of a drug (whichever is longer) prior to Visit 1 and for the duration of the study.

3.4.22 Treatment with strong CYP3A4 inhibitors:

- Cardiovascular: verapamil and diltiazem
- Antibiotics: clarithromycin, telithromycin, troleandomycin, erythromycin
- HIV: protease inhibitors (ritonavir, indinavir, saquinavir, nelfinavir, amprenavir, lopinavir)
- Antifungals: itraconazole, ketoconazole, voriconazole, fluconazole
- Antidepressants: nefazodone

3.4.23 Other prohibited medications :

- Oral hypoglycemics: tolbutamide, chlorpropamide
- Ergot derivatives: dihydroergotamine, ergonovine, ergotamine, methylergonovine
- Neuroleptics: pimozide
- Antiarrhythmics: amiodarone, bepridil, flecainide, lidocaine, mexilitine, quinidine, propafenone
- Immune modulators: cyclosporine, tacrolimus, sirolimus.
- Miscellaneous: theophylline, quetiapine, risperidone, tacrine, clozapine, atomoxetine

3.4.24 Treatment with strong CYP3A4 inducers:

- Anticonvulsants: phenytoin, carbemazepine, Phenobarbital, oxcarbazepine
- HIV antiretrovirals: efavirenz, nevirapine
- Antibiotics: rifampin (rifampicin), rifabutin, rifapentine
- Miscellaneous: St. John's Wort, modafinil, pioglitazone, troglitazone

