5.5.5.3 Prohibited Medications

Participants must be instructed not to take any medications (over-the-counter or other products) during the protocol treatment period without prior consultation with the investigator. The investigator should instruct the participant to notify the study site about any new medications he/she takes after the start of study drug. All medications (other than study drug) and significant non-drug therapies (including physical therapy and blood transfusions) taken within 28 days of starting study treatment through the 30-day safety follow up visit should be reported on the CRF.

- Subjects should not receive other anti-cancer therapy [cytotoxic, biologic, radiation, or hormonal (other than leuprolide or other GnRH agonists)] while on treatment in this study.
- No chronic treatment with systemic steroids or other immunosuppressive agents are allowed. Topical or inhaled corticosteroids are allowed.
- Medications that inhibit strongly CYP3A4 may result in increased plasma pazopanib and everolimus concentrations. Selection of an alternate concomitant medication with no or minimal potential to inhibit CYP3A4 is required. **Strong CYP3A4 inhibitors which are prohibited include:**

- Antibiotics: clarithromycin, telithromycin, troleandomycin
- HIV: protease inhibitors (ritonavir, indinavir, saquinavir, nelfinavir, amprenavir, lopinavir)
- Antifungals: itraconazole, ketoconazole, voriconazole, fluconazole
- Antidepressants: nefazodone
- **Specific recommendation regarding non-dihydropyridine calcium channel blockers (verapamil and diltiazem)**: co-administration of pazopanib with calcium channel blockers may result in increased plasma concentrations of the calcium channel blocker. Non-dihydropyridine calcium channel blockers, verapamil and diltiazem, have potential depressive effects on cardiac conduction and contractility. When pazopanib therapy is initiated, the administration of an anti-hypertensive or anti-anginal agent other than verapamil and diltiazem is recommended in the setting of a prolonged PR interval (greater than 200 msec), sinus bradycardia (less than 60 beats per minute), or second or third degree heart block, unless the subject has a permanent pacemaker.

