- **Strong CYP3A4 inducers** may decrease plasma pazopanib concentrations. Selection of an alternate concomitant medication with no or minimal enzyme induction potential is required. **Drugs that induce CYP3A4 and may decrease pazopanib and everolimus plasma concentrations include (but are not limited to):**
 - Glucocorticoids: cortisone (>50 mg), hydrocortisone (>40 mg), prednisone (>10 mg), methylprednisolone (>8 mg), dexamethasone (>1.5 mg)
 - Anticonvulsants: phenytoin, carbamezepine, phenobarbital, oxcarbazepine
 - HIV antivirals: efavirenz, nevirapine
 - Antibiotics: rifampin (rifampicin), rifabutin, rifapentine
 - Miscellaneous: St. John's Wort, modafinil, pioglitazone, troglitazone

Everolimus may affect the response to vaccinations making the response to the vaccination less effective. Live vaccines should be avoided while a patient is treated with everolimus.

Vaccinations

Immunosuppressants may affect the response to vaccination and vaccination during treatment with everolimus may therefore be less effective. The use of live vaccines should be avoided during treatment with everolimus Examples of live vaccines are: intranasal influenza, measles, mumps, rubella, oral polio, BCG, yellow fever, varicella, and TY21a typhoid vaccines.

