3. Agents containing hydrogen peroxide, iodine, and thyme derivatives may tend to worsen mouth ulcers. It is preferable to avoid these agents.
4. Antifungal agents must be avoided unless a fungal infection is diagnosed. In particular, systemic imidazole antifungal agents (ketoconazole, fluconazole, itraconazole, etc.) should be avoided in all patients due to their strong inhibition of everolimus metabolism, thereby leading to higher everolimus exposures. Therefore, topical

antifungal agents are preferred if an infection is diagnosed. Similarly, antiviral agents such as acyclovir should be avoided unless a viral infection is diagnosed.

Note: Stomatitis/oral mucositis should be appropriately graded using the functional grading given on the NCI-CTC for adverse events, CTCAE v 4.0. Dose reductions are made according to section 6.3.1 (Non-hematological toxicity) and Section 6.3.3.

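### The caution list allows conditional use of fluconazole, which Section 5.5.5.3 prohibits, and of three anticonvulsants for which that section, on its more natural reading, requires an alternative

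*Combined protocol and SAP*

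**What the plan says.** Two neighbouring subsections under Drug Interactions (5.5.5) set the on-study rules.

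- **Permitted Medications – Use with Caution.** This is printed as 5.5.2, a number already used for palliative radiotherapy. It comes after 5.5.5 and directly before 5.5.5.3, so 5.5.5.2 was evidently meant. Its item 1, on everolimus, names "moderate CYP3A4 inhibitors (such as erythromycin, fluconazole, calcium channel blockers, benzodiazepines") and then continues: "moderate CYP3A4 inducers (e.g. carbamazepine, phenobarbital, phenytoin) should also be avoided if possible, or used subject to caution". Its examples of caution are more frequent safety monitoring and temporary interruption of everolimus.
- **Prohibited Medications (5.5.5.3).** The list of prohibited strong CYP3A4 inhibitors includes "Antifungals: itraconazole, ketoconazole, voriconazole, fluconazole". The bullet on strong CYP3A4 inducers says: "Selection of an alternate concomitant medication with no or minimal enzyme induction potential is required". The list below it includes "Anticonvulsants: phenytoin, carbamezepine, phenobarbital, oxcarbazepine".

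Three other places bear on the same drugs. Exclusions 3.2.22 and 3.4.22 name fluconazole as a strong inhibitor, and 3.2.24 and 3.4.24 name the three anticonvulsants as strong inducers. Section 6.2.1 says that "systemic imidazole antifungal agents (ketoconazole, fluconazole, itraconazole, etc.) should be avoided in all patients due to their strong inhibition of everolimus metabolism". Section 2.1.1.4 sends the reader to Section 5.4.5 for the list of inhibitors and inducers, but Section 5.4 ends at 5.4.2.

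**The concern.** A site looking up one of these drugs during treatment gets a different answer depending on which subsection it opens. A site that stops at the caution list could start a drug that the next subsection bars, and could reasonably believe it was following the protocol.

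The consequences differ by drug. Section 5.5.5.3 says that strong inhibitors may increase concentrations of both pazopanib and everolimus, so fluconazole is a toxicity concern. It says that inducers may decrease concentrations of both, so the anticonvulsants are mainly a loss-of-activity concern.

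A need for fluconazole on study is foreseeable. Mucositis was reported in 33% of phase I patients (Section 2.3), Section 6.2.1 anticipates fungal infection when mouth ulcers are managed, and Section 6.2.5 says everolimus predisposes to fungal infection.

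**Working it through.** There is no planned figure to reproduce. The check compares the drugs named in each place, with spelling variants merged.

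**Step 1. Drugs named in item 1.** Two inhibitors (erythromycin, fluconazole) and three inducers (carbamazepine, phenobarbital, phenytoin): 2 + 3 = 5. It also names two classes, calcium channel blockers and benzodiazepines.

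**Step 2. The two on-study rules side by side.**

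| Drug | Item 1 of the caution list | Section 5.5.5.3 | Entry exclusions, both cohorts |
|---|---|---|---|
| Fluconazole | Moderate; avoid if possible, or caution | Prohibited by name as a strong inhibitor | Strong inhibitor |
| Carbamazepine | Moderate; same rule | Listed under the strong-inducer bullet; alternative required | Strong inducer |
| Phenobarbital | Moderate; same rule | As carbamazepine | Strong inducer |
| Phenytoin | Moderate; same rule | As carbamazepine | Strong inducer |
| Erythromycin | Moderate; same rule | Not listed | Strong inhibitor |

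Four of the five named drugs (4/5 = 80%) have a stricter rule in 5.5.5.3.

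**Step 3. How firm each conflict is.** For fluconazole it is explicit: the same drug is conditionally usable in one subsection and prohibited in the next. For the anticonvulsants it depends on reading the 5.5.5.3 list as a list of strong inducers. The line introducing that list mentions CYP3A4 induction but not strength. Two facts favour the strict reading. First, the list sits under the strong-inducer bullet of the Prohibited Medications section. Second, apart from its glucocorticoid line, the list names 4 anticonvulsants + 2 HIV drugs + 3 antibiotics + 4 miscellaneous = 13 agents, and Section 3.4.24 names the same 13 as strong inducers.

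**Step 4. Which text is out of line.** For fluconazole, Sections 3.2.22, 3.4.22, 5.5.5.3 and 6.2.1 all describe strong inhibition. For the anticonvulsants, 3.2.24 and 3.4.24 say strong and 5.5.5.3 files them there. Only item 1 says moderate. No precedence rule is stated, and the reference in Section 2.1.1.4 points to a section that does not exist.

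**Step 5. Context for fluconazole only.** The phase I table in Section 2.3 gives a mean everolimus AUC of 335 ng*h/mL with pazopanib, against 238 in a cited study: 335/238 − 1 = +41%. The accompanying text says +100%, which these means do not reproduce. This is a cross-study comparison in 5 patients by the text, or 3 + 2 + 1 = 6 by the tumour types listed. It suggests that an inhibitor would act on exposure that may already be raised. It does not show by how much, and it has no bearing on the inducers.

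**The case against.** The best case on the other side has four parts.

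- **The entry rules already deal with this.** All four drugs are exclusions in both cohorts, and 3.4.21 requires prohibited drugs to be stopped before Visit 1 and to stay stopped throughout the study. This largely stands. A reader might infer that patients could be kept on these drugs, but the documents do not support that. What remains is a new prescription on study.
- **Consultation is required.** Section 5.5.5.3 requires the investigator to be consulted before any new medication, and Section 5.5.5 calls for the Principal Investigator to be alerted to agents that affect CYP450. Item 1 itself says first to avoid these drugs, Section 6.2.1 prefers topical antifungals, and 3.4.4 does not allow anticonvulsants in patients with treated brain metastases. These lower the risk, but whoever is consulted reads the same two rules. Section 6.2.5 stops everolimus for invasive systemic fungal infection only, and does not mention pazopanib.
- **Item 1 concerns everolimus only.** True, but 5.5.5.3 covers both drugs, and combination patients take both.
- **The anticonvulsants could be read as moderate, within a general list of inducers.** That reading is available, so the anticonvulsant conflict should be held less firmly than the fluconazole one. The evidence in step 3 favours the strict reading.

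Two wider inferences are tempting. One is that the general sentence "Substances that induce or inhibit CYP3A4 may alter the pharmacologic effects of pazopanib and should be used with" caution is a further contradiction. A general caution followed by a specific prohibited list is ordinary drafting, and the specific list can be taken to govern. The other is that the drugs in 3.4.23 that reappear in the caution list, or the different entry and on-study rules for erythromycin, verapamil and diltiazem, are errors. Section 3.4 applies at screening and 5.5.5.3 names none of the 3.4.23 drugs, so stricter rules at entry than on study may be deliberate. These are at most queries to the sponsor.

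**Conclusion.** The plan is internally inconsistent on four drugs: explicitly for fluconazole, and by placement and cross-reference for carbamazepine, phenobarbital and phenytoin. Item 1 of the caution list is the text to correct. This conclusion assumes that the stricter rule is the intended one, as the entry exclusions, 5.5.5.3 and (for fluconazole) 6.2.1 indicate.

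The practical exposure is limited to drugs newly started on study and is reduced by the safeguards above. The documents give no rate of such prescribing and no size for the interaction, so no effect on toxicity or response can be calculated. A reader might infer that the trial's statistical conclusions are in doubt, but nothing here touches the sample size, the error rates or the response analysis. It is a modest safety and conduct correction, worth making because it is so cheap.

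**What to change.** 1. In item 1 of Permitted Medications – Use with Caution, delete fluconazole, carbamazepine, phenobarbital and phenytoin, so that 5.5.5.3 governs all four. This leaves the moderate-inducer phrase without examples; it can stand as a class, or the sponsor can supply others.
2. In Section 2.1.1.4, change both references from 5.4.5 to 5.5.5. Cite the caution list by title in the amendment, because its printed number is duplicated.
3. Optionally, ask the sponsor to confirm that the entry and on-study rules are meant to differ for erythromycin, verapamil and diltiazem, and for the 3.4.23 drugs that reappear in the caution list.

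The cost is a wording amendment and a slightly narrower choice of concomitant drugs: a patient who needs one of the four must use an alternative or stop study treatment. The deletion adds no restriction beyond 5.5.5.3 on its strict reading.
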